Subjects must have been on oral or parenteral MTX therapy for ≥ 3 months, on a stable MTX dose for ≥ 4 weeks prior to the first dose of study drug (15 to 25 mg/week; or ≥ 10 mg/week in subjects who are intolerant of MTX at doses ≥ 12.5 mg/week), and must remain on a stable dose throughout the study; the MTX dose may be decreased only for safety reasons. In addition, all subjects should take a dietary supplement of oral folic acid (or equivalent) throughout study participation. Folic acid dosing and timing of regimen should be followed according to the Investigator's instructions. Starting at the Week 26 visit (after Week 26 assessments have been performed) and thereafter, initiation of or change in background RA medication(s) including, corticosteroids, non-steroidal anti-inflammatory drugs (NSAIDs), acetaminophen/paracetamol is allowed as per local label. Starting at Week 48 (after Week 48 assessments have been performed) and thereafter, initiation of or change in csDMARDs is allowed as per local label (restricted to oral or parenteral MTX, sulfasalazine, hydroxychloroquine, chloroquine and leflunomide, and restricted to concomitant use of up to 2 csDMARDs except the combination of MTX and leflunomide).

Starting at the Week 48 and thereafter, at least 20% improvement in BOTH TJC AND SJC compared to baseline is required to remain on study drug. Anyone who does not fulfill this criterion at 2 consecutive visits (starting at Week 48) must be discontinued from study drug.

Subjects with prior exposure to at most one biologic disease-modifying anti-rheumatic drug (bDMARD) (except ADA) for RA may be enrolled in the study (up to 20% of total number of subjects) after the required washout period is satisfied and if they have a) limited bDMARD exposure (< 3 months), OR b) response to a bDMARD but had to

discontinue that bDMARD due to intolerability (regardless of treatment duration) (for washout periods. These subjects will be equally stratified across all treatment groups. Subjects, who are considered bDMARD-inadequate responders (lack of efficacy), as determined by the Investigator, are not eligible.

Rescue therapy will be offered to subjects who meet the following criteria:

Placebo:

- Subjects who do not achieve a $\geq 20\%$ improvement in TJC and SJC at Weeks 14, 18, or 22 compared to baseline will be switched to blinded Upadacitinib treatment.

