10.0 Safety Analysis

10.1 General Considerations

Safety analyses will be carried out using the Safety Analysis Set. There are three sets of planned safety analysis: safety analysis up to Week 14, safety analysis up to Week 26 censored at treatment switching, and long-term safety analysis. Missing safety data will not be imputed.

10.1.1 Safety Analysis up to Week 14

Standard safety analysis by the "as treated" treatment groups of placebo, ADA 40 mg EOW, Upadacitinib 15 mg QD groups will be performed on safety data up to Week 14. No protocol-defined treatment switching will occur prior to this time point.

The standard safety analyses will include reporting of adverse events (AEs), laboratory, and vital signs measurements. Frequency tables of subjects with treatment-emergent adverse events (TEAEs) by system organ class (SOC) and by preferred term (PT) as in the Medical Dictionary for Regulatory Activities (MedDRA) dictionary will be provided by treatment group. Mean changes from baseline in all continuous laboratory parameters and vital signs variables at each visit will be summarized by "as treated" treatment group. Frequency tables of subjects meeting criteria for potentially clinically significant vital sign values and for potentially clinically significant laboratory values will be provided by treatment group.

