10.1.2 Safety Analysis up to Week 26 Censored at Treatment Switching

Standard safety analysis by the "as treated" treatment groups of placebo, ADA 40 mg EOW, Upadacitinib 15 mg QD groups will be performed on safety data up to Week 26.

For subjects who are rescued to a different study drug prior to Week 26, safety data will be censored at the time of treatment switching.

The standard safety analyses will include reporting of adverse events (AEs), laboratory, and vital signs measurements. Frequency tables of subjects with treatment-emergent adverse events (TEAEs) by system organ class (SOC) and by preferred term (PT) as in the Medical Dictionary for Regulatory Activities (MedDRA) dictionary will be provided by treatment group. Mean changes from baseline in all continuous laboratory parameters and vital signs variables at each visit will be summarized by "as treated" treatment group. Frequency tables of subjects meeting criteria for potentially clinically significant vital sign values and for potentially clinically significant laboratory values will be provided by treatment group.

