10.1.3 Long-Term Safety Analysis

Long-term safety analyses include reporting of AE rate adjusted by cumulative exposure, mean change from baseline in laboratory parameters and vital sign variables, and frequency of potentially clinically significant laboratory and vital signs values.

The treatment-emergent adverse event (TEAE) rate per 100 patient-years of exposure will be presented by actual treatment received (i.e., exposed to) at the time of AE (treatment exposure for subjects switching treatments is described in Section 8.1). Listing of subjects with TEAEs by SOC and PT will be provided. Frequency tables and listings of subjects meeting criteria for potentially clinically significant vital sign values and for potentially clinically significant laboratory values will be provided by actual treatment received at the time of event.

For long-term analysis of TEAEs and potentially clinically significant laboratory or vital signs values, two sets of summaries will be provided, namely "summary based on all study drug exposure" and "summary based on long-term study drug."

Summary based on all study drug exposure:

This summary will take into account safety data under the exposure of each study drug for each subject, i.e., an all-inclusive summary. The summary will be grouped by study drug as follows (and as illustrated in the figure below):

[figure not shown]
1. Placebo

2. Any ADA 40 mg EOW

This includes ADA exposure from subjects starting on ADA 40 mg EOW and subjects rescued from Upadacitinib 15 mg QD to ADA 40 mg EOW

3. Any Upadacitinib 15 mg QD

This includes Upadacitinib 15 mg QD exposure from subjects starting on Upadacitinib 15 mg QD, subjects rescued/switched from placebo to Upadacitinib 15 mg QD, and subjects rescued from ADA 40 mg EOW to Upadacitinib 15 mg QD

UPA = upadacitinib; ADA = adalimumab; PBO = placebo; WK = week; trt = treatment

* Treatment switching may occur at Week 14, 18, 22 or 26. Treatment switching in the graph is positioned between Week 14 and Week 26 for illustration purposes.

1. Belongs to group 1: Placebo.
2. Belongs to group 2: Any ADA 40 mg EOW.
3. Belongs to group 3: Any Upadacitinib 15 mg QD.

Summary based on long-term study drug:

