10.2.1 Analysis of Short-Term Adverse Events

Two sets of analysis will be conducted for short-term adverse events, namely "safety analysis up to Week 14" and "safety analysis up to Week 26 censored at treatment switching" as outlined in Section 10.1.1 and Section 10.1.2. Adverse events will be summarized by frequency and percentages by "as treated" treatment groups of placebo, ADA 40 mg EOW and Upadacitinib 15 mg QD.

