10.2.1.1 Adverse Events Overview

The number and percentage of subjects experiencing TEAEs will be summarized by "as treated" treatment group and overall for the following AE categories.

- All TEAEs
- Treatment-emergent serious adverse events (SAEs)
- Treatment-emergent severe adverse events

- TEAEs reasonably possibly related to study drug
- TEAEs of special interest
- TEAEs leading to discontinuation of study drug
- TEAE leading to death

Additional AEs may be considered for tabulation/summary based on recommendations from Clinical and Safety as deemed appropriate.

For TEAEs of special interest, the point estimate and 95% CI (using normal approximation) will be provided for the treatment difference in AE percentages.

As a sensitivity analysis, the AE overview summary will be repeated by randomized treatment groups. In this summary, all AEs with an onset date after the first dose of study drug will be included, regardless of whether the AE occurred more than 30 days (or 70 days) after the last dose of study drug.

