10.2.2 Analysis of Long-Term Adverse Event Rates

Long-term adverse event rates will be analyzed using event rates adjusted by cumulative exposure and will be based on the actual treatment received at the time of AE occurrence. Two sets of summaries, "summary based on all study drug exposure" and "summary based on long-term study drug," respectively, will be provided following the treatment groups as described in Section 10.1.3.

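### Week 26 safety percentages are compared after censoring at rescue without allowing for unequal follow-up, which could make upadacitinib look worse than placebo when the hazards are the same

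*SAP*

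**What the plan says.** SAP 4.2 sets the rescue rule. Placebo subjects without the required "improvement in TJC and SJC at Weeks 14, 18, or 22 compared to baseline will be switched to blinded Upadacitinib treatment". Adalimumab and upadacitinib subjects cross over on the same joint criterion at the same visits.

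SAP 10.1.2 defines a safety set to Week 26. For subjects rescued before then, "safety data will be censored at the time of treatment switching". SAP 10.2.1 covers this set and the Week 14 set together: "Adverse events will be summarized by frequency and percentages by" as-treated group. For AESIs, SAP 10.2.1.1 adds that "the point estimate and 95% CI (using normal approximation) will be provided for the treatment difference in AE percentages". No person-time or time-to-event measure is specified for either short-term set.

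Two other analyses bear on the point. For the Week 14 set, SAP 10.1.1 notes that "No protocol-defined treatment switching will occur prior to this time point". For the long-term set, SAP 10.2.2 says "Long-term adverse event rates will be analyzed using event rates adjusted by cumulative exposure". SAP 10.1.3 adds that the "rate per 100 patient-years of exposure will be presented by actual treatment received", and its all-exposure summary includes a placebo group. SAP 10.2.2.1 gives a 95% CI for the AESI rate difference in that analysis.

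**The concern.** A rescued subject contributes roughly 14, 18 or 22 weeks of a 26-week window but still counts as a full subject in the denominator. The arm with more rescue therefore has less time in which to record an event, and its percentage is lower for that reason alone.

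Rescue follows from failing a 20% improvement in joint counts, which is part of ACR20. SAP 4.3 plans for a 37% ACR20 response on placebo and a 22-point advantage for upadacitinib. If the drug works as planned, placebo should be censored earlier.

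Comparing safety with placebo and with adalimumab is the third Period 1 objective. The affected table is the only one that sets the three starting groups side by side over the placebo-controlled 26 weeks, and it carries a formal interval for AESIs.

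**Working it through.** The documents state no rescue fraction, event hazard or bias figure, so there is no planned number to reproduce.

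**Inputs from the documents**
- Rescue at Weeks 14, 18 or 22 (SAP 4.2), and 600 subjects in each of the upadacitinib and placebo arms.
- Planned ACR20 of 37% on placebo and 37 + 22 = 59% on upadacitinib (SAP 4.3), so non-response of 63% and 41%.

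**Assumptions**
- The same constant hazard h of a first event in both arms.
- A fraction s rescued, all at Week 14 (day 98); everyone else is followed to day 182.

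**Formula.** Expected percentage = (1 − s)(1 − exp(−h·182/365.25)) + s(1 − exp(−h·98/365.25)).

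**Worked case, h = 1 per year.** The two bracketed risks are 0.3924 and 0.2353. Placebo with s = 0.35: 0.65 × 0.3924 + 0.35 × 0.2353 = 33.7%. Upadacitinib with s = 0.15: 0.85 × 0.3924 + 0.15 × 0.2353 = 36.9%. The ratio is 1.093 and the gap 3.1 points, with no true difference.

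| h per year | 35% v 15% rescued: placebo, upadacitinib | ratio; gap (points) | 45% v 20% rescued: placebo, upadacitinib | ratio; gap (points) |
|---|---|---|---|---|
| 0.02 | 0.83%, 0.92% | 1.110; 0.09 | 0.79%, 0.90% | 1.145; 0.11 |
| 0.04 | 1.66%, 1.84% | 1.109; 0.18 | 1.57%, 1.79% | 1.145; 0.23 |
| 0.5 | 18.7%, 20.6% | 1.101; 1.9 | 17.8%, 20.2% | 1.134; 2.4 |
| 1 | 33.7%, 36.9% | 1.093; 3.1 | 32.2%, 36.1% | 1.122; 3.9 |
| 2 | 55.5%, 59.9% | 1.078; 4.3 | 53.4%, 58.8% | 1.101; 5.4 |

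**Other pairings of the same fractions.** Taking 35% v 20% and 45% v 15% as well widens the relative excess to 5.8-16.0% for h = 0.5-2 and to 8.2-17.4% for h = 0.02-0.04.

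**Anchored on planned ACR20.** Suppose 25%, 50%, 75% or 100% of ACR20 non-responders in both arms fail the joint criterion at Week 14. For rare events the ratio is close to the ratio of mean exposure, (26 − 12s) weeks in each arm:
- 25%: 24.77/24.11 = 1.03
- 50%: 23.54/22.22 = 1.06
- 75%: 22.31/20.33 = 1.10
- 100%: 21.08/18.44 = 1.14

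The 25% case at h = 2 gives the smallest relative excess, 2.0% (59.7% v 60.9%).

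**Overall range.** The relative excess runs from about 2% to 17%. At h = 0.02-0.04 the absolute gap runs from 0.025 points (25% case) to 0.27 points (45% v 15%).

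**What shrinks it**
- Equal rescue: ratio 1.00.
- Later rescue: if all non-responders (63% v 41%) are spread evenly over the three visits, the rare-event ratio falls from 1.14 to 1.08.
- Front-loaded events: if the hazard halves after Week 14, 30% v 10% rescued gives (14 + 6 × 0.9)/(14 + 6 × 0.7) = 19.4/18.2 = 1.07, against 24.8/22.4 = 1.11 with a constant hazard.

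**Against sampling error, 600 per arm.** In the tabulated scenarios the gap at h = 1 is 1.1-1.4 standard errors of the difference. At h = 2 with 45% v 20% it is 1.9. For rare events it is about 0.2-0.3.

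**After the change.** With events divided by on-drug time over the same window, the expected rate ratio under equal constant hazards is 1.00 whatever the rescue fractions.

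**The case against.** The strongest reply is that other planned analyses already answer most of this. The Week 14 tables repeat the comparison before any protocol-defined switching. Placebo exposure ends by Week 26, so the placebo column of the all-exposure summary is essentially the censored placebo experience, expressed per 100 patient-years and with AESI rate-difference intervals. That stands as mitigation, but it leaves a gap:
- The Week 14 set omits Weeks 14-26.
- The upadacitinib column in the all-exposure summary pools randomized subjects with those switched from placebo and adalimumab, over the whole study.
- The summary by long-term study drug has no placebo group.
- The sensitivity overview by randomized group in SAP 10.2.1.1 repeats the same counts and percentages.

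It is also fair to say that every rescue fraction above is assumed, and that 35% v 15% is a wider gap than the ACR20 anchor suggests. Applying one fraction of non-responders to both arms (35% v 22.8%, 45% v 29.3%) gives 4.7-8.4% for h = 0.5-2 and 6.7-9.1% for rare events. A reader might infer that the plan will make upadacitinib look some 8-15% worse; the documents do not support an unconditional figure.

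A reader might also infer a bias against adalimumab. The rescue rule is the same in that arm and no adalimumab rescue rate is given, so neither direction nor size follows.

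Finally, the expected bias against placebo makes upadacitinib look worse. It does not hide harm in that comparison, and no efficacy or multiplicity decision depends on it.

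**Conclusion.** The point holds conditionally. The Week 26 set combines censoring at rescue with crude percentages and a formal AESI interval. If placebo is rescued more often, which is the direction implied by the planned ACR20 gap, the comparison is biased against upadacitinib even with equal hazards.

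The size rests on equal constant hazards, assumed rescue fractions and all rescue at Week 14. For common events the bias can approach two standard errors in the less favourable scenarios. For rare AESIs it is small in absolute terms and well inside sampling error, so a relative excess quoted alone would overstate its importance there.

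What is missing is narrow: an exposure-adjusted comparison of the three arms over the same 26 weeks. The documents do not show that the crude percentages must be withdrawn. This is a change that should be made, given its low cost and its bearing on a stated objective, but it does not threaten the trial's main conclusions.

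**What to change.** For the Week 26 set censored at switching, add one of the following for all TEAEs, SAEs and AESIs:
- rates per 100 patient-years, either first-event incidence rates or the event rates already defined in SAP 10.2.2; or
- Kaplan-Meier or cumulative incidence to Week 26.

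Give the AESI difference and its 95% CI on the chosen scale, and show exposure by arm beside the crude percentages, which may stay as description. State which numerator is used: SAP 10.2.2 counts repeat events, whereas a percentage counts each subject once, so first-event rates stay closer to the present table.

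The cost is a little more programming, since the rate formula and the AESI rate-difference interval already exist for the long-term analysis. The change corrects unequal follow-up only. Rescue is triggered by non-response, so censoring may be informative; neither rates nor Kaplan-Meier estimates remove that, and the table should say so.

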10.1.3 Long-Term Safety Analysis

Long-term safety analyses include reporting of AE rate adjusted by cumulative exposure, mean change from baseline in laboratory parameters and vital sign variables, and frequency of potentially clinically significant laboratory and vital signs values.

The treatment-emergent adverse event (TEAE) rate per 100 patient-years of exposure will be presented by actual treatment received (i.e., exposed to) at the time of AE (treatment exposure for subjects switching treatments is described in Section 8.1). Listing of subjects with TEAEs by SOC and PT will be provided. Frequency tables and listings of subjects meeting criteria for potentially clinically significant vital sign values and for potentially clinically significant laboratory values will be provided by actual treatment received at the time of event.

For long-term analysis of TEAEs and potentially clinically significant laboratory or vital signs values, two sets of summaries will be provided, namely "summary based on all study drug exposure" and "summary based on long-term study drug."

Summary based on all study drug exposure:

This summary will take into account safety data under the exposure of each study drug for each subject, i.e., an all-inclusive summary. The summary will be grouped by study drug as follows (and as illustrated in the figure below):

[figure not shown]
1. Placebo

2. Any ADA 40 mg EOW

This includes ADA exposure from subjects starting on ADA 40 mg EOW and subjects rescued from Upadacitinib 15 mg QD to ADA 40 mg EOW

3. Any Upadacitinib 15 mg QD

This includes Upadacitinib 15 mg QD exposure from subjects starting on Upadacitinib 15 mg QD, subjects rescued/switched from placebo to Upadacitinib 15 mg QD, and subjects rescued from ADA 40 mg EOW to Upadacitinib 15 mg QD

UPA = upadacitinib; ADA = adalimumab; PBO = placebo; WK = week; trt = treatment

* Treatment switching may occur at Week 14, 18, 22 or 26. Treatment switching in the graph is positioned between Week 14 and Week 26 for illustration purposes.

1. Belongs to group 1: Placebo.
2. Belongs to group 2: Any ADA 40 mg EOW.
3. Belongs to group 3: Any Upadacitinib 15 mg QD.

Summary based on long-term study drug:

"Summary based on long-term study drug" considers safety data from the study drug for which a subject will remain on long-term for the rest of the study. For subjects who did not switch treatment during the study, all safety data under the original study drug will be summarized. For subjects who switched treatment during the study, safety data under the study drug that they switched to (i.e., the second study drug) will be summarized; in this case, safety data from the first study drug is only short-term and therefore will not be included in this summary. The treatment groups for this summary are as follows (and as illustrated in the figure below):

1. Upadacitinib 15 mg QD, switched from Placebo

This includes Upadacitinib 15 mg QD exposure from subjects who switched from placebo to Upadacitinib 15 mg QD (either due to rescue treatment switch or systematic switch at Week 26)

2. Upadacitinib 15 mg QD, no treatment switching

This includes Upadacitinib 15 mg QD exposure from subjects starting on Upadacitinib 15 mg QD and who did not switch study treatment due to rescue

3. ADA 40 mg EOW, no treatment switching

[figure not shown]
This includes ADA 40 mg EOW exposure from subjects starting on ADA 40 mg EOW and who did not switch study treatment due to rescue

4. Upadacitinib 15 mg QD, switched from ADA

This includes Upadacitinib 15 mg QD exposure from subjects who switched from ADA 40 mg EOW to Upadacitinib 15 mg QD

5. ADA 40 mg EOW, switched from Upadacitinib

This includes ADA 40 mg EOW exposure from subjects who switched from Upadacitinib 15 mg QD to ADA 40 mg EOW

UPA = upadacitinib; ADA = adalimumab; PBO = placebo; WK = week; trt = treatment

* Treatment switching may occur at Week 14, 18, 22 or 26. Treatment switching in the graph is positioned between Week 14 and Week 26 for illustration purposes.

1. Belongs to group 1: Upadacitinib 15 mg QD, switched from Placebo.
2. Belongs to group 2: Upadacitinib 15 mg QD, no treatment switching.
3. Belongs to group 3: ADA 40 mg EOW, no treatment switching.
4. Belongs to group 4: Upadacitinib 15 mg QD, switched from ADA.
5. Belongs to group 5: ADA 40 mg EOW, switched from Upadacitinib.

In addition to the analyses described above, mean changes from baseline in all continuous laboratory parameters and vital signs variables at each visit will be summarized by "as treated" treatment group sequences defined as follows:

1. Placebo → Upadacitinib 15 mg QD
2. ADA 40 mg EOW
3. ADA 40 mg EOW → Upadacitinib 15 mg QD
4. Upadacitinib 15 mg QD
5. Upadacitinib 15 mg QD → ADA 40 mg EOW

